1. PROJECT TITLE

Evaluation of AV delay optimization vs. intrinsic conduction in patients with long PR intervals receiving dual chamber pacemakers for symptomatic bradycardia.

3. FACILITIES

UCSD Medical Center including Encinitas Clinical and Echocardiography Facilities

4. ESTIMATED DURATION OF THE STUDY

24 months

5. LAY LANGUAGE SUMMARY OR SYNOPSIS

Short and long term effects of different pacemaker settings on hemodynamics such as cardiac output and on right ventricular remodeling and other chamber dimensions, in patients with dual chamber pacemakers for symptomatic bradycardia with long PR intervals.

6. SPECIFIC AIMS

To evaluate the acute effects on cardiac output with a long AV delay allowing for intrinsic conduction as compared to an echocardiographically optimized AV delay during dual chamber pacing, and then to follow the patients to see if there are any remodeling changes related to a high degree of RV pacing.

7. BACKGROUND AND SIGNIFICANCE

Cardiac pacing is the only effective treatment for symptomatic sinus node dysfunction. Most patients with preserved left ventricular function receive dual chamber pacemakers; however, right ventricular apical pacing can have detrimental effects on left ventricular function due to the abnormal electrical and mechanical activation pattern of the ventricles.

Many patients receiving dual chamber pacemakers for symptomatic bradycardia have prolonged intrinsic AV conduction (first degree AV block), and as a result, will receive a significant amount of ventricular pacing if programmed at physiologic AV intervals. As an alternative, many pacemakers can be programmed to minimize ventricular pacing at the expense of allowing longer AV delays; however, these long AV delays are also not physiologic and may also lead to reduced cardiac output.

The main scientific questions being addressed in this study are to evaluate the acute effects on cardiac output with a long AV delay allowing for intrinsic conduction as compared to an echocardiographically optimized AV delay during dual chamber pacing, and then to follow the patients to see if there are any remodeling changes related to a high degree of RV pacing.

8. PRELIMINARY STUDIES/PROGRESS REPORT

There is a paucity of data in the type of patients being enrolled in this study. There is only one small study (reference 3) which did show a benefit to AV delay optimization with dual chamber pacing. However, this study was done before the new pacing modalities with MVP and the like that allow for longer AV intervals, and also before the data with regard to the potential detrimental effects of RV pacing. As such, this prior study (reference 3) had no follow up data on what would happen with the increased pacing over time, and is also

outdated as there are newer pacemaker programming options that were not in existence at the time of that investigation.

9. RESEARCH DESIGN AND METHODS

Study Design:

This will be a randomized, prospective clinical trial. All patients enrolled will undergo echocardiographic evaluation with AV delay optimization which will be compared to intrinsic conduction, and thus patients will serve as their own controls with respect to the acute hemodynamic data.

After observing the acute hemodynamic effects of AV delay optimization vs. intrinsic conduction, patients will be randomized in a 1:1 ratio by order of enrollment to either the echocardiographically optimized AV delay vs. with a long fixed AV delay allowing for intrinsic conduction. All patients will then get follow up echocardiograms at 6 months after randomization to assess if there are any remodeling changes associated with a higher burden of RV pacing. Patients will be monitored for any adverse events with routine clinic visits one-two weeks after implantation and programming and at 3 month intervals or as needed as per standard of clinical care.

Methods:

Patients who have AV conduction with long PR intervals (>230 msec) with preserved LV function who are receiving dual chamber pacemakers for symptomatic bradycardia will be evaluated by echocardiography evaluating baseline systolic and diastolic function as well as for mechanical dyssynchrony. Baseline aortic TVI, as a surrogate of cardiac output, will be measured and will be compared with aortic TVI with AAI pacing at 70 bpm and 90 bpm and with DDD pacing 70 bpm and 90 bpm at the optimal AV delay achieved with atrio-ventricular pacing at each heart rate.

To determine the optimal AV delay, the bradycardia device will be programmed to the DDD mode, and all patients will undergo echocardiographic analysis at varying AV delays. Measurement of continuous-wave aortic Doppler flow velocities in the apical five chamber view at baseline and at eight AV intervals: 220, 200, 180, 160, 140, 120, 100, 80 ms. will be done. After 20 cardiac cycles at each AV delay, measurements will be made on the final three to four cardiac cycles and averaged. The optimal AV delay will be defined as the AV delay associated with the largest average aortic Doppler VTI.

Measurements of diastolic dysfunction and dyssynchrony will also be re-evaluated with AAI pacing and with DDD pacing at optimized AV delays to evaluate the effects of pacing on these parameters as well.

Patients will then be randomized in a 1:1 ratio by order of enrollment to either the echocardiographically optimized AV interval or to a long-fixed AV delay that will allow for intrinsic conduction. Patients will have routine clinical follow up at 3 month intervals in the pacemaker clinic as per our usual standard of care, and then will have a comprehensive follow up 2D echo at 6 months after randomization to assess for any potential changes related to RV pacing including, RV function, LV function, LV end-systolic volume, LV end-diastolic volumes, wall thickness, and dyssynchrony as assessed by tissue Doppler imaging.

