10. HUMAN SUBJECTS

A total of 40 patients will be recruited from the Cardiology Electrophysiology clinics of either gender for Echocardiography and AV delay optimization.

Inclusion Criteria: (all must be met)

1. Must have Symptomatic bradycardia requiring dual chamber pacemaker

2. PR interval of > 230 msec
3. Must give written informed consent
4. Must be at least 18 years old

Exclusion Criteria: (presence of any one or more)

1. Complete or high grade AV block
2. Persistent Atrial Fibrillation

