14. POTENTIAL RISKS

The published literature indicates that there are no known immediate or delayed or long-term risks from ultrasound imaging using the ultrasound output levels and techniques for routine ultrasound exams.

The AV optimization involves temporary programming changes, and an electrophysiologist will be present throughout the programming. In the unlikely event that a patient does not tolerate a change in pacemaker mode, the pacemaker will be reset to its initial mode and that patient's study will be terminated.

After final programming, patients will be followed and pacemaker adjustments made as per routine clinical care. Follow up echocardiograms will be obtained to ensure there are no significant changes in cardiac function with pacing. If any changes are noted, the pacemakers will be adjusted as per routine clinical practice.

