15. RISK MANAGEMENT PROCEDURES AND ADEQUACY OF RESOURCES

Patients will be monitored for any adverse events with routine clinic visits 1-2 weeks after initial implantation of the pacemaker and at 3 month intervals or as needed as per standard of clinical care. Patients will also be enrolled and followed by home remote monitoring if possible (whether or not this is possible depends on the brand of pacemaker implanted, and if they have a home telephone line).

The arrhythmia clinic is staffed by two nurse practitioners and a dedicated technician for pacemaker interrogations and related issues. We currently follow over 1,000 patients with implanted intracardiac devices. The clinic number [contact] is answered daily from 8 AM to 5 PM, and the nurse practitioners are always available during this time period. The nurse practitioners discuss all phone calls with the primary electrophysiologist and make notes into the EPIC electronic medical record.

After business hours, the answering machine provides the number for the electrophysiology fellow and attending on call, whom are available 24 hours daily for urgent issues.

There are also two research assistants in the electrophysiology division who can assist with the reporting of any adverse events to the Human Studies Committee.

The study will be funded by existing funds provided by [name] for the purpose of performing echocardiograms.

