26. IMPACT ON STAFF

All research activities will be done in the echocardiography lab by the investigators. Pacemaker management and follow up will be done as per routine standard of care.

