DIVISION OF CARDIOVASCULAR MEDICINE
[contact]
NIGHTS & WEEKENDS: [contact]
[contact]

OFFICE OF:
[name].
PROFESSOR OF MEDICINE
DIRECTOR EP PROGRAM
[name]
[name]
[contact]

Date: November 15, 2024

To: Whom it may Concern

Re: Project # 130663
NCT02154750

Evaluation of AV Delay Optimization vs. Intrinsic Conduction in Patients with Long PR Intervals
Receiving Dual Chamber Pacemakers for Symptomatic Bradycardia.

Statistical Analysis Variables are displayed as the mean \pm 1SD. Categorical variables are presented as number and percentage. For comparisons of the baseline categorical variable between groups, chi-square test was used. Wilcoxon signed-rank test was used to compare each variable between baseline and 6 months after randomization. The change in each parameter was compared between each group using the Mann-Whitney U test. A p value of < 0.05 was considered statistical significance. Analyses were performed using SPSS version 23 (IBM corporation, Chicago, Illinois).

If there are any questions or concerns regarding this submission, please contact [name], Research Coordinator, at [contact]. Thank you for your consideration in this matter.

Sincerely,

A handwritten signature in black ink, appearing to read "[name]".

[name] /bb
Professor of Medicine
Director Cardiac Electrophysiology Program
University of California, San Diego

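### Allocation is stated only as 1:1 in enrollment order, with no random sequence or concealment; if that was literal, the 6-month between-arm comparison is open to selection bias

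*Protocol*

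**What the plan says.** Protocol Section 9, under Study Design, describes a randomized, prospective trial. After the acute echo study, "patients will be randomized in a 1:1 ratio by order of enrollment to either the echocardiographically optimized AV delay" or to a long fixed AV delay. The Methods part repeats the rule: "Patients will then be randomized in a 1:1 ratio by order of enrollment". That is all the protocol says about how arms are assigned. I found no mention of a computer list, blocks, a list-holder, envelopes or a central system. Sections 2 and 21 were not in the text I read, so a description there cannot be excluded, but the section that states the rule is present and has none.

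Other relevant places:
- Section 10 plans 40 patients, with "PR interval of > 230 msec" among the entry criteria.
- Section 11 places eligibility review and consent in the clinic, before the acute study and therefore before assignment.
- Section 14 provides for exits during the acute testing: "In the unlikely event that a patient does not tolerate a change in pacemaker mode, the pacemaker will be reset to its initial mode". Participation then ends for the person concerned.
- The SAP gives the between-arm analysis: "The change in each parameter was compared between each group using the Mann-Whitney U test". It names no covariate adjustment. It does specify a chi-square comparison of baseline categorical variables between groups. For continuous variables it says only "Variables are displayed as the mean" with SD, and does not say whether these are shown by arm.

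**The concern.** The trial has two aims (Section 6). The acute cardiac-output comparison uses each patient as his or her own control and does not depend on allocation. The 6-month remodeling comparison is between arms and does.

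If enrollment order itself fixes the arm, anyone who knows the last assignment knows the next one. That knowledge could influence who is approached, when a patient is enrolled, or whether a borderline intolerance during the acute study leads to an exit. The plan does not say whether such an exit uses up a place in the sequence. A prognostic difference created in this way would be read as an effect of the AV-delay setting. Section 7 lists drawbacks of both settings, so the direction of any bias cannot be predicted.

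**Working it through.** There is no document figure to reproduce: the sample size comes without an effect size, SD or power. The check has a textual part and an illustrative simulation.

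**1. Text.** The two statements of the rule in Section 9 agree, and neither says how the order becomes an arm. Two readings fit: (a) a deterministic rule such as alternation; (b) a random list whose entries are used in enrollment order. Nothing else in the documents decides between them.

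**2. Predictability under reading (a).** With 40 patients alternated, every assignment after the first is known: 39 of 40. Counting half a correct guess for the first gives 39.5, against about 20 for simple randomization.

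**3. Size of bias.** From the documents: N = 40 (20 per arm), Mann-Whitney U, alpha 0.05. Two-sided testing is assumed, because the SAP does not state sidedness. Also assumed: no true effect, outcome SD 1, a share q of entries steered, and a correlation rho between the steering variable and 6-month change. Two steering models were used:
- *Median-side*: a steered patient always falls on the favoured side of the median. The mean of a half-normal is 0.798, so the between-arm bias is about 2 × 0.798 × q × rho × 39/40.
- *Better-of-two*: the more favourable of two candidates is taken. The mean of the larger of two normals is 0.564, so the bias is about 2 × 0.564 × q × rho × 39/40.

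For q = 0.50 and rho = 0.5, the median-side bias is 2 × 0.798 × 0.25 × 0.975 = 0.39 SD, and the better-of-two bias is 2 × 0.564 × 0.25 × 0.975 = 0.27 SD.

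Simulated type I error (20,000 replicates; Monte Carlo SE about 0.15 points at 5% and 0.3 points at 22%):

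| q | rho | Median-side | Better-of-two |
|---|---|---|---|
| 0.10 | 0.1 / 0.3 / 0.5 | 4.8 / 4.9 / 5.4% | 4.8 / 5.0 / 5.3% |
| 0.25 | 0.1 / 0.3 / 0.5 | 5.0 / 6.3 / 8.9% | 5.3 / 5.9 / 6.9% |
| 0.50 | 0.1 / 0.3 / 0.5 | 5.5 / 11.0 / 22.5% | 5.3 / 7.6 / 13.1% |

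Without steering the rate is 4.6-5.1%. Repeat runs agree to within about a percentage point, so I round the range for q of 0.25-0.50 and rho of 0.3-0.5 to 6-23% (median-side) and 6-14% (better-of-two).

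**4. Feasibility of steering.** Forty patients over the 24 months of Section 4 is 40/24 = 1.7 per month. Better-of-two needs two candidates at once. Median-side needs on average one refusal or deferral per steered place, or about 20 at q = 0.50 (0.50 × 40). Screening volume is not given, so neither model can be called likely.

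**5. Random list, past assignments visible, q = 0.5, rho = 0.5, median-side steering on the guessed arm.** An unblocked list with 20 per arm gives 5.4%. Random blocks of 4/6/8 give 6.5%, and blocks of 2/4/6 give 7.4%.

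**6. Adjustment (N = 40, median-side, q 0.10-0.50).** Regression on arm plus the steering variable gives 4.8-5.1% if that variable is measured exactly, and 4.8-7.2% at an assumed reliability of 0.7.

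**The case against.** The strongest reply is that no allocation flaw is shown. Section 9 calls the trial randomized and uses the word again in both statements of the rule, and a random list is normally used in enrollment order. If that was done, one sentence closes the point. This stands, and it is why the concern is conditional. A reader might infer that alternation was used, or that bias occurred; the documents support neither. But the one rule actually written down names only order, and a reader cannot tell from it whether the label is earned.

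A reader might also take Section 26 ("All research activities will be done in the echocardiography lab by the investigators") to mean that the investigators held the allocation. It does not show that. It is a statement about staff impact and does not address who allocates. Nor is it exhaustive, since Section 11 puts consent in the clinic.

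A third reply is that the larger error rates rest on assumed steering. This also stands. No document gives a steering share, or a correlation between anything known before consent and 6-month change. With light steering the error rate is essentially nominal. The 22.5% figure is the harshest cell of the harsher model and should not be quoted as the expected error rate.

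Finally, the SAP is not silent on baseline comparability, because it compares categorical variables between groups. What it leaves open is a by-arm display of continuous variables such as PR interval, EF and the echo measures.

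**Conclusion.** The concern holds in conditional form. The stated allocation rule does not establish random, concealed assignment. If it was followed literally, the 6-month comparison is exposed to selection at entry and at exits before assignment. The effect on type I error would be negligible with light steering and material only with substantial steering on a prognostic variable, within the ranges shown above; those ranges rest on alternation, 20 per arm and assumed steering inputs. The point should be fixed because the rule is explicit, the exposed comparison is a stated aim, and the remedy is cheap. Confidence is medium, because only the study team knows which method was used.

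**What to change.** **If allocation is not complete.** In both places in Section 9, replace the enrollment-order phrase with: *by the next entry on a computer-generated 1:1 random list (unblocked, or with undisclosed randomly varying block sizes), held by existing staff not involved in consent or echo and released only after eligibility and the acute echo data are recorded*. Section 15 notes that "There are also two research assistants in the electrophysiology division"; one of them could hold the list if not involved in consent or echo. Release after the acute study also keeps exits during that study blind to the arm.

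**If allocation is complete**, as the past-tense SAP letter of November 2024 suggests, state how arms were assigned and concealed. If a concealed random list was used, that statement is enough. If assignment was order-based:
1. Call the trial quasi-randomized and limit the 6-month conclusion accordingly.
2. Show PR interval, EF and baseline echo values by arm, in addition to the categorical comparison already in the SAP.
3. Report exits before assignment, with reasons.
4. Keep the Mann-Whitney test and add one sensitivity analysis, labelled post hoc, that adjusts the 6-month value for its baseline value. Say that it cannot remove selection on unmeasured factors.

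**Cost.** Before allocation: a wording change, a one-off list and minor administrative work. After allocation: one statement and, only if assignment was order-based, a table, an account of exits and one analysis. No extra patients or visits are needed. The trial may end up with a less favourable design label.

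### Baseline aortic VTI is compared, as a stand-in for cardiac output, with VTI at paced rates of 70 and 90 bpm with no allowance for heart rate; AAI versus DDD at equal ventricular rate is unaffected

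*Protocol*

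**What the plan says.** The acute aim in Protocol Section 6 begins "To evaluate the acute effects on cardiac output with a long AV delay allowing for intrinsic conduction". Section 7 states the comparison as "a long AV delay allowing for intrinsic conduction as compared to an echocardiographically optimized AV delay during dual chamber pacing". The Study Design part of Section 9 describes it as "AV delay optimization which will be compared to intrinsic conduction, and thus patients will serve as their own controls".

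The Methods part of Section 9 gives the measurements: "Baseline aortic TVI, as a surrogate of cardiac output, will be measured and will be compared with aortic TVI with AAI pacing at 70 bpm". The sentence goes on to AAI pacing at 90 bpm and to DDD pacing at the same two rates, "at the optimal AV delay achieved with atrio-ventricular pacing at each heart rate". Baseline is therefore the named comparator for four paced states. Its heart rate is not given, and nothing says that it is matched to 70 or 90 bpm.

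The SAP does not fill the gap. Its only paired test is a Wilcoxon signed-rank test of baseline against six months, and its between-group test is a Mann-Whitney U test on changes. It names no acute comparison and does not mention heart rate.

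**The concern.** VTI is a per-beat quantity. Cardiac output also depends on how many beats there are per minute, and in this experiment the rate is changed by design. If a patient's own rate at baseline is slower than the paced rate, VTI should be lower during pacing even when output is the same.

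A raw comparison of baseline with paced VTI therefore contains a rate effect that is not an output effect. A reader who takes the surrogate at face value could conclude that pacing lowers output when it leaves output unchanged or raises it. Acute output is one of the two questions that the trial sets itself, so the misreading would matter.

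**Working it through.** **Inputs.**
- Paced rates of 70 and 90 bpm, under both AAI and DDD: Protocol Section 9, Methods.
- Baseline rate: not in the documents. I assume 50, 60 and 70 bpm. Rates below the paced rates are plausible because Section 10 enrols patients with symptomatic bradycardia.
- Outflow area: assumed constant within a patient during the session.

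The documents give no figure on this point to reproduce.

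**Formula.** Output = VTI × outflow area × heart rate. With area constant within a patient,

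VTI(paced) / VTI(baseline) = [output(paced) / output(baseline)] × [rate(baseline) / rate(paced)].

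**Step 1: output unchanged.** The change in VTI is rate(baseline) / rate(paced) − 1.

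| Assumed baseline rate | VTI change at 70 bpm | VTI change at 90 bpm |
|---|---|---|
| 50 bpm | 50/70 − 1 = −28.6% | 50/90 − 1 = −44.4% |
| 60 bpm | 60/70 − 1 = −14.3% | 60/90 − 1 = −33.3% |
| 70 bpm | 70/70 − 1 = 0% | 70/90 − 1 = −22.2% |

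**Step 2: VTI unchanged.** The implied change in output is rate(paced) / rate(baseline) − 1. For baselines of 50, 60 and 70 bpm this is +40.0%, +16.7% and 0% at 70 bpm, and +80.0%, +50.0% and +28.6% at 90 bpm. Equal VTI does not mean equal output.

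**Step 3: can the sign reverse?** Let output truly rise by 10% from a baseline of 60 bpm. VTI changes by 1.10 × 60/70 − 1 = −5.7% at 70 bpm and by 1.10 × 60/90 − 1 = −26.7% at 90 bpm. A real gain appears as a loss.

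**Step 4: AAI against DDD at the same ventricular rate.** The rate ratio is 1, so the VTI ratio equals the output ratio and the artefact is zero. The choice of AV delay is unaffected for the same reason. The rule is "The optimal AV delay will be defined as the AV delay associated with the largest average aortic Doppler VTI", and if the sweep is made at one paced rate, VTI ranks the delays as output would.

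**The case against.** The strongest reply is that the main acute question is rate-matched by design. Sections 6 and 7 ask about intrinsic conduction against an optimized AV delay. Section 9 then provides AAI and DDD at the same two rates, with the delay optimized at each. The same pairing serves the other acute measures: "Measurements of diastolic dysfunction and dyssynchrony will also be re-evaluated with AAI pacing and with DDD pacing at optimized AV delays". This stands. A reader might infer that the acute aim is itself confounded because baseline could be the intrinsic-conduction comparator. The documents do not support that, since separate AAI states exist for the purpose.

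A second reply is that baseline may have been rate-matched. The optimization text records "flow velocities in the apical five chamber view at baseline and at eight AV intervals", and optimization is done at each rate, so a baseline at each rate is a possible reading. It would remove the artefact, but the text does not say so.

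A third reply concerns direction and necessity. A reader might infer that the artefact could equally be a spurious rise, or that one baseline can never match two rates and so some contrast must be confounded in every patient. Neither follows. A programmed 70 bpm is a lower limit. If the patient's own stable rate is above it, AAI pacing is inhibited and DDD tracks the atrium, so the ventricular rate stays near baseline and the artefact is about zero. An own rate of 90 bpm or more would give no mismatch at either setting. That is unlikely in this population, but it is not excluded.

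Finally, multiplying VTI by rate gives an output index but does not separate mode from rate: from baseline to DDD at 90 bpm, both may change. This also stands, and it limits what the remedy may claim.

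**Conclusion.** The concern holds for the baseline-versus-paced comparisons and no further. As written, they use a per-beat measure as a surrogate of output across states whose rates are neither matched nor accounted for. For assumed baselines of 50 to 70 bpm, the artefact at unchanged output runs from −29% to 0% at 70 bpm and from −44% to −22% at 90 bpm. It is large enough to reverse the sign of a 10% gain.

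These figures illustrate the size of the artefact and do not predict the data. They rest on the assumed baseline rates, a constant outflow area and a ventricular rate equal to the paced rate. The artefact is absent if baseline was rate-matched, or if the patient's own rate was at or above the set rate.

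The acute aim is not invalidated, because AAI against DDD at equal ventricular rate answers it. That comparison still has to be written down: the Methods sentence names baseline as the comparator, and the SAP names no acute comparison at all.

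**What to change.** Add to the SAP:

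> Raw VTI is compared only between states at equal ventricular rate. The acute Aim 1 analysis is the within-patient difference in VTI, DDD at the optimized AV delay minus AAI, at each of 70 and 90 bpm, by Wilcoxon signed-rank test. Comparisons with baseline use VTI × measured ventricular rate, are descriptive, and are read as the combined effect of rate and mode, not of mode alone. Where rate was not stored, baseline comparisons are not reported as evidence on cardiac output.

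The protocol or the report should also state at what rate baseline VTI was recorded, and whether there was one baseline or one for each paced rate. If it was rate-matched, one sentence settles the point.

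The SAP is written in the past tense. If the acute data have already been analysed, the remedy is re-analysis or disclosure, and the report should say that the comparison was specified afterwards. No new recordings are needed.

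The cost is SAP wording and one multiplication per recording used in a baseline comparison. With one baseline and four paced states, that is 5 per patient, or 5 × 40 = 200 for the planned 40 patients. The downside is slightly more analysis work, and the loss of baseline comparisons as evidence on output where rate was not stored.

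### Per-beat aortic TVI at baseline, rate unstated, is compared as cardiac output with paced TVI at 70 and 90 bpm without correction for ventricular rate

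*Protocol*

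**What the plan says.** Protocol section 9 (Methods) sets out the acute measurements. It states: "Baseline aortic TVI, as a surrogate of cardiac output, will be measured". That value "will be compared with aortic TVI with AAI pacing at 70 bpm and 90 bpm", and with DDD pacing at the same two rates, "at the optimal AV delay achieved with atrio-ventricular pacing at each heart rate". No mode or rate is given for the baseline reading.

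The section then describes the search for the optimal delay with the device in DDD: "Measurement of continuous-wave aortic Doppler flow velocities in the apical five chamber view at baseline and at eight AV intervals", from 220 down to 80 ms. The delay with the largest average value is taken as optimal. The mode and rate of the baseline reading are not given here either.

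Section 10 requires of every patient: "Must have Symptomatic bradycardia requiring dual chamber pacemaker". It excludes complete and high-grade AV block but does not name type I second-degree block (Mobitz I).

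The SAP letter names tests for baseline categorical variables, for baseline versus 6 months, and for change between groups. It names no analysis of the acute TVI readings. Neither document multiplies TVI by rate, asks for the actual ventricular rate to be recorded, or says what to do when conduction in AAI is not 1:1.

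**The concern.** Cardiac output is flow per minute; TVI reflects flow per beat. Between two readings in one patient, TVI ranks output correctly only if the ventricle beats at the same rate in both. The Protocol controls this by setting AAI and DDD to common rates, but the control does not reach the baseline reading. That reading has no stated rate, comes from patients treated for bradycardia, and is compared with readings at two different paced rates.

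If baseline is slower than the paced rate, TVI per beat can fall while output per minute is unchanged or higher. A report that pacing lowered TVI relative to baseline could then be taken as a fall in output when output had risen.

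A second, conditional route exists. If AAI pacing outruns AV conduction and beats drop, the ventricular rate in AAI is below the set rate. AAI then looks better per beat than it is per minute, which favours intrinsic conduction over the optimized delay.

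**Working it through.** The documents give no figure to reproduce here. The check uses one identity and the stated paced rates.

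**Inputs**
- Paced rates p = 70 and 90 bpm (Protocol section 9).
- Baseline rate r: not given. Assumed values of 50, 60 and 70 bpm show the range.
- Conduction ratio in AAI: not given. Assumed 5:4, 4:3 and 3:2 for a single patient with dropped beats.
- Outflow area taken as constant within a patient, so output is proportional to TVI × ventricular rate.

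**Step 1. Baseline versus paced, output unchanged.** Setting TVI(paced) × p = TVI(baseline) × r gives an apparent TVI change of r/p − 1.

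| Assumed baseline | At 70 bpm | At 90 bpm |
|---|---|---|
| 50 bpm | 50/70 − 1 = −28.6% | 50/90 − 1 = −44.4% |
| 60 bpm | 60/70 − 1 = −14.3% | 60/90 − 1 = −33.3% |
| 70 bpm | 0% | 70/90 − 1 = −22.2% |

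**Step 2. A true output gain of 10% at 70 bpm.** The apparent change is 1.10 × r/70 − 1.
- r = 50: 1.10 × 50/70 − 1 = −21.4%.
- r = 60: 1.10 × 60/70 − 1 = −5.7%.

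**Step 3. Gain needed before TVI rises at all.** This is p/r − 1.
- r = 60: 16.7% at 70 bpm and 50.0% at 90 bpm.
- r = 50: 40.0% at 70 bpm and 80.0% at 90 bpm.

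A larger gain does show as a rise. A 20% gain at 70 bpm from a 60 bpm baseline reads 1.20 × 60/70 − 1 = +2.9%.

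**Step 4. Smallest possible worst case for one baseline rate.** Below 70 bpm the distortion at 90 bpm exceeds 22.2%. Above 90 bpm the distortion at 70 bpm exceeds 90/70 − 1 = 28.6%. Between them, the larger of the two is smallest where they are equal in size:
- r/70 − 1 = 1 − r/90
- r = 2 × 70 × 90 / (70 + 90) = 78.75 bpm
- 78.75/70 − 1 = +12.5% and 78.75/90 − 1 = −12.5%

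So at least one of the two comparisons is distorted by 12.5% or more, whatever the baseline rate.

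**Step 5. AAI versus DDD at the same set rate.** With 1:1 conduction the ventricular rates are equal and the correction factor is 1.00. With dropped beats at a set rate of 90 bpm, the TVI ratio AAI/DDD at equal output is 90 divided by the ventricular rate.

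| Conduction | Ventricular rate | TVI ratio AAI/DDD |
|---|---|---|
| 5:4 | 90 × 4/5 = 72.0 | 1.25 |
| 4:3 | 90 × 3/4 = 67.5 | 1.33 |
| 3:2 | 90 × 2/3 = 60.0 | 1.50 |

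These describe one hypothetical patient each.

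**Step 6. What does not change.** Choosing the optimal delay compares readings within one paced rate. The 6-month echocardiogram is listed as assessing ventricular function, volumes, wall thickness and dyssynchrony, not acute TVI.

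**The case against.** The strongest defence is that the named acute question is optimized delay versus intrinsic conduction, not baseline versus paced. Fixing 70 and 90 bpm in both modes is the design's rate control, and with 1:1 conduction it works exactly. This stands, and it confines the point. It does not remove it, because section 9 explicitly plans the baseline comparison and calls TVI a surrogate for output in the same sentence.

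Dropped beats in AAI are also only a possibility. The Protocol describes patients with first-degree block, excludes complete and high-grade block, and has an electrophysiologist present during programming (section 14). That section covers a mode the patient does not tolerate. It does not provide for recording symptomless dropped beats or adjusting for them. No frequency is given, so no cohort-level effect can be claimed.

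A reader might go further and infer that the acute aim is left unmeasured. The aim names "a long AV delay allowing for intrinsic conduction as compared to an echocardiographically optimized AV delay during dual chamber pacing" and half the patients are randomized to "a long-fixed AV delay that will allow for intrinsic conduction". Yet the longest DDD delay in the sweep, 220 ms, is shorter than any qualifying conduction time ("PR interval of > 230 msec"). The documents do not support treating this as an error:
- The design paragraph of section 9 states the acute contrast as optimization against intrinsic conduction, and AAI at matched rates supplies it.
- When conduction is 1:1 within the long delay, a DDD reading at that delay would duplicate AAI.
- The baseline reading in the sweep follows the instruction to program DDD. Its mode is undefined, so a DDD reading with intrinsic conduction cannot be ruled out.

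Nor may a reader conclude that every paced setting must look worse than a slow baseline; Step 3 shows that a large enough gain still appears as a rise.

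Finally, the SAP is dated November 2024 and written in the past tense, so acquisition may be over. That limits the remedy, not the point.

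**Conclusion.** The point holds and is minor. As written, the baseline-versus-paced TVI comparison cannot be read as a change in cardiac output. The 12.5% floor needs only the two stated paced rates, a single baseline rate and a constant outflow area. The larger figures rest on assumed baselines of 50 or 60 bpm. All are equal-output benchmarks, not predictions of what the trial will show. At those baselines a modest true gain can take the wrong sign.

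The AAI-versus-DDD contrast is affected only in patients whose AAI conduction is not 1:1, at an unknown frequency that may be zero. Confidence is medium because the baseline reading is undefined: a baseline paced at 70 bpm, for example, would leave the 70 bpm comparison intact.

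**What to change.** 1. State the mode and rate of the baseline reading.
2. For each reading, note on the research form the actual ventricular rate and whether atrial beats conduct 1:1, both taken from the tracing.
3. Compare TVI × actual ventricular rate. Where AAI is not 1:1, average over whole conduction groups; a fixed run of three or four beats need not match a group.
4. Name AAI as the acute intrinsic-conduction comparator. No added recordings at a long DDD delay are needed.

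If acquisition is finished, apply the correction wherever the rate can be read from the tracing or form. Where it cannot, do not interpret baseline-versus-paced TVI as a change in output.

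The cost is a few extra entries per reading and one multiplication in the analysis. No stated test changes, because the SAP names none for the acute readings. Retrospective correction may be incomplete, since Protocol section 16 has patient identifiers destroyed once data are collected, which could prevent linking back to tracings.
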